12.1 Potential Benefits

Study participants may benefit from the positive feelings associated with participating in a study of the health effects of the oil spill that may be of value to their community. In addition, the knowledge gained from this study may have a significant impact on future public health responses to similar disasters. It is also possible that participants may benefit directly from public health responses that are based on early findings from this study. Finally, participants may benefit from receiving results of medical evaluations and health care referrals that they may not otherwise receive.

12.2 Potential Risks

The questionnaires and study procedures associated with the clinical exam study present minimal risks to study participants. Adverse events associated with study procedures are expected to be uncommon and limited to mild and transient discomforts. In order to

minimize risks to participants, all study procedures will be conducted by qualified, experienced, and well-trained research staff.

The questionnaires are based on instruments that are widely used in epidemiological studies and administered in the baseline enrollment effort. The main risk in questionnaire administration involves questions about sensitive health topics or personal experiences that may be traumatic. Participants will be told that they can skip any questions that make them feel uncomfortable or end the interview at any time. Questions related to mental health and distress and drug abuse may be more stressful than other questions, but as described above, staff will be appropriately trained and systems have been put in place to deal with any issues that may arise. Participants will also be warned of the possibility of loss of privacy should their de-identified data distributed through controlled access procedures be linked back to them in ways that cannot be foreseen at present.

Pulmonary function testing is considered safe. The primary risk, which is exceedingly rare, is fainting in older participants with impaired lung function. We minimize the chance that this rare event will occur by using very conservative exclusions for pulmonary function testing. To further minimize risk of fainting, pulmonary function testing is done in a seated position, and study staff will be trained to look for signs of dizziness or other problems and to stop the maneuver if necessary. We will also exclude participants from testing who have extremely high blood pressure or rapid pulse rates. The risk of infection is all but eliminated by using disposable mouthpieces (spirettes). These disposable mouthpieces have the additional protection of having a built-in bacterial filter.

The only other health risk is associated with the use of albuterol, a bronchodilator, which may cause some jitteriness and increased heart rate. In order to minimize these risks, participants with abnormal blood pressure or heart rate will not undergo spirometry testing, and all participants will be observed for spirometry-related adverse events prior to discharge from the clinic.

There may be some minor discomfort associated with blood collection, including temporary pain, bruising, or swelling at the phlebotomy site. Fainting during blood collection is exceedingly rare.

13 Adverse Event Reporting

Adverse events that are related to clinical procedures and that require clinical intervention are expected to be very uncommon and occur in less than 1% of the study population. Any clinically-significant, procedural-related adverse events requiring medical attention will be reported to the IRBs during the annual continuing review.

Study staff may encounter participants who report or display symptoms of acute, pre-existing medical or mental health conditions that are not related to participation in the study. The results of study procedures, such as blood pressure measurement, may indicate the need for immediate medical attention for poorly controlled or previously undiagnosed illness. Clinic personnel may also observe signs that suggest the existence of reportable social or abusive behaviors or encounter participants who are experiencing mental health distress, suicidal ideation, or homicidal thoughts. Any pre-existing health problem, mental health distress, or social situation that requires a call to 911, local authorities, or social services will also be reported to the NIEHS IRB and local site IRBs as

an adverse event at the time of continuing review. The report will include information on the outcome of the actions taken in response to the event.

A clinically significant adverse event related to study procedures will be reported as a serious adverse event if it is life threatening, causes persistent or significant disability, leads to death, or requires medical or surgical intervention to prevent one of these outcomes. The principal investigator will be responsible for reporting all clinically significant serious adverse events related to study procedures to the NIEHS and clinical site IRBs within 24 hours of receiving notification that an event occurred.

Unanticipated problems are defined as any incident, experience, or outcome that meets all of the following criteria:

- unexpected in terms of nature, severity, or frequency given (a) the research procedures that are in the protocol and informed consent and (b) the characteristics of the subject population being studied;
- related or possibly related to participation in the research;
- suggests that the research places subjects or others at a greater risk of harm (including physical, psychological, economic, or social harm) than was previously known or recognized

Serious unanticipated problems and serious protocol deviations will be reported to the NIEHS and CD as soon as possible but not more than seven days after the Principal Investigator first learns of the event. Not-serious unanticipated problems will be reported to the IRB and CD as soon as possible but not more than 14 days after the Principal Investigator first learns of the event. Not serious protocol deviations will be reported to the IRB as soon as possible but not more than 14 days after the Principal Investigator first learns of the event. Sites will report these events to their IRBs according to local requirements.

14 Timeline

We plan to initiate clinical examinations in May 2014. The initiation phase will begin with a run-in period to assess the feasibility of operational plans. The run-in will last for approximately four months and will be followed by ramp-up in visit rates that will allow us to complete all exams within approximately 18 months of start-up.

During the four month run-in phase, we will pilot test all aspects of the study, as currently planned, including study procedures, data collection systems, and operational plans. In addition, we will monitor participation rates, implementation of procedures, and overall timing of the clinic visit. We also aim to gain a more accurate reflection of how distance and remuneration impact cohort members' willingness to be involved, as well as overall participant motivation to complete the exam. We will seek IRB approval for any protocol changes that need to be made based on our experience during the run-in phase.

We plan to ramp up the study in August 2014 to ensure that all visits are completed over the next 12-14 months. Depending on when we obtain final IRB approval from all participating sites, we will adjust the launch and ramp-up dates as necessary. However, we anticipate that the run-in phase and study ramp-up will take 4 months and 12-14 months respectively. We will implement any necessary changes during the ramp-up

phase in response to our experience during the run-phase. We may ramp up the study sooner, if we find that operational activities stabilize more quickly than current anticipated.

15 Practice Exams

To improve the quality of exams, we will test Biomedical Surveillance Clinical Examination procedures with a small number of adult volunteers who are not enrolled in the GuLF STUDY. About 20 participants age 21 or older will be invited to take part in practice exams to test and evaluate instructions and procedures for clinical examinations.

Volunteers will be asked to come to one of the two study clinic sites. Exams will be conducted using the procedures described above. However, for practice exams, minimal personal contact information will be recorded. Contact information will be destroyed upon completion of the practice exam and the stored data and samples will be anonymized. Information collected during the practice exam will be used to help interpret the results of any tests that are performed. All samples will be linked to the information that is collected by an ID number only.

We will store samples using the storage methods described above. At a later date, we will use the anonymous data and samples to develop future tests or for laboratory quality control measures. Samples provided may be used for quality control of specimen collection, handling, storage and testing for the GuLF STUDY. These samples may also be used to understand the effects of long-term storage, to serve as a comparison or as quality control samples and to evaluate the feasibility and reliability of specific studies and laboratory tests. Analyses of samples may be done at laboratories at the National Institutes of Health or in the laboratories of research collaborators or contractors at other institutions. Samples may be kept indefinitely and analyzed for other tests at a later date. They may also be disposed at any time at the discretion of the investigators or shared with other researchers.

Staff at each site will recruit volunteers using word of mouth. Staff will schedule appointments, administer the informed consent, collect data and specimens, administer exam tests, and provide participants with reports, referrals and remuneration. Participants for practice exams will receive a copy of the consent form and a staff member and witness will sign that the consent was explained and agreed to by the participant. Consent forms will be marked with a participant ID so that forms, data and samples can be linked. Up to twenty-five practice exams will be completed at each site.

16 Expanded Blood Collection and Lymphocyte Isolation

To explore emerging hypotheses related to exposures to constituents of oil, dispersants, and oil-dispersant mixtures, and to spill-related psychosocial stress, the GuLF STUDY plans to collect additional blood samples from a subset of approximately 300 participants at Louisiana State University based on their estimated exposure. This subset of participants will not overlap with those selected for quality control blood collections.

Clinic staff will use a “butterfly” blood collection set to collect an additional 24 mL of blood at LSU by venipuncture into four 6 mL Yellow-Top ACD-B Tubes.

After collection, clinic personnel will bring the collected biospecimens to the clinic laboratory for processing. Laboratory personnel will isolate polymorphonuclear cells/lymphocytes from the whole blood specimen using a discontinuous gradient separation media (Histopaque) in Greiner Leucosep® porous barrier centrifugation tubes. Separated cells will be washed **two** times with a buffer (Hank's Balance Salt Solution) and cryopreserved in a freeze-mix solution including 50% heat-inactivated fetal bovine serum HIFBS, 15% DMSO, and 35% RPMI at a controlled rate of approximately -1°C per minute to -80°C for storage at that temperature prior to shipment.

The isolated lymphocytes will be shipped to the CPL using the same procedures as described above in section 6.12.3.

References

1. United States. National Commission on the BP Deepwater Horizon Oil Spill and Offshore Drilling., *Deep water : The Gulf oil disaster and the future of offshore drilling : Report to the President* 2011, Washington, D.C.: National Commission on the BP Deepwater Horizon Oil Spill and Offshore Drilling : For sale by the Supt. of Docs., U.S. G.P.O. xiii, 380 p.
2. Jamail, D. *Environmental Protection Agency? Residents of the US Gulf Coast say their pleas for help and transparency continue to be ignored by regulators.* Al Jazeera 2010 12/6/2010 [cited 2013 3/30/2013]; Available from: <http://www.aljazeera.com/indepth/2010/12/2010125113825735197.html>.
3. King, B.S. and J.D. Gibbins, *Health Hazard Evaluation of Deepwater Horizon Response Workers.*, in *Health Hazard Evaluation Report, HETA 2010-0115 & 2010-0129-31382011*, National Institute for Occupational Safety and Health. p. 20.
4. Aguilera, F., et al., *Review on the effects of exposure to spilled oils on human health.* J Appl Toxicol, 2010. 30(4): p. 291-301.

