Biological Specimen Collection [†]	15 min.	
 • Hair, Toenail Clippings[*] and Urine Collection • Provide training and materials for serial saliva samples (for a subset) and collect baseline saliva sample • Venous blood collection, (including quality control and other additional collections for subsets) and finger stick for Hemoglobin A1c and lipid testing

Activity	Time	Notes
Peripheral Nervous System Tests [†]	25 min.	
 • Visual Acuity • Visual Contrast Sensitivity • Handgrip Strength • Vibrotactile Threshold Testing • Standing Steadiness (Postural Stability) • Single Leg Stance • Long Distance Corridor Walk (400m) • Trailmaking
Neurobehavioral Tests	50 min.	
 • Finger Tapping • Symbol-Digit • Simple Reaction Test • Digit Span • Match to Sample • Continuous Performance • Progressive Ratio
eNO	10 min.	
 • Exhaled Nitric Oxide
Pulmonary Function Testing ^{**†}	30 min.	
 • Pre/post-bronchodilator spirometry
Mental Health Assessment	40 min.	
 • Questionnaire administration and referral, if needed
Substance Abuse Questionnaire	10 min.	
 • Self-administered computer-based questionnaire
Biological Specimen Processing [†]	N/A	
 • Process, aliquot, label, and temporarily store specimens
Report of Findings [†]	10 min.	
 • Handout provided with clinically relevant findings and recommendations for seeking additional care, if indicated • Referral provided, if needed
Check-Out and Remuneration [†]	5 min.	
 • Remuneration
Clean-up and Specimen Shipping [†]	N/A	
 • Samples packed and shipped in batches by clinical staff
Total time	4hrs. 0 min.	

** If toenail specimens cannot be collected during the visit, the participant will receive toenail collection instructions and a prepaid self-addressed envelope to return toenail samples to the central processing laboratory.*

*** Pulmonary measures will be collected in the order of eNO, then spirometry because spirometry may affect eNO measurements. [39]*

† Exam components that will be included in the abbreviated exam.

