Mental health referrals will be based on responses to the PHQ-9, the PC-PTSD, and the GAD-7. We will use validated cutoff points to systematically assess mental health distress and provide real-time referrals. Follow-up calls will be placed to all participants who receive a mental health referral to available mental health services in their area to determine if services were obtained and to provide additional information regarding health services, if necessary.

Staff will also be trained to respond to more serious signs of mental health distress, such as suicidal or homicidal thoughts, that require additional interventions. Participants who express such thoughts will be assessed for signs of acute distress and asked if they have plans, intentions, and means to act on their thoughts. Based on

these assessment findings, study staff will take appropriate action, as summarized in Table 3 below.

Table 3. Action Plan for Responding to Suicidal and Homicidal Thoughts

Individual at Risk	Imminent Danger*	Action
Self	No	
 Continue study activities, depending on level of emotional distress Offer a mental health care referral and follow-up call for all referrals
Self	Yes	
 End study activities Refer to emergency care at local community services if available, or through national Hotline Escalate to study managers and investigators Follow-up call for all referrals
Other	No	
 Continue study activities, depending on level of emotional distress Offer a health care referral and follow-up call for all referrals
Other	Yes	
 End study activities Call 911 Escalate to study managers and investigators Follow-up call for all referrals

* Homicidal or suicidal thoughts combined with plans, intention, or means to act on thoughts.

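### Practice-exam volunteers' contact details are destroyed when the exam is completed, so a volunteer referred for mental health cannot receive the follow-up call that Section 6.10 requires

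*Protocol*

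**What the plan says.** The relevant text is all in Addendum 3 of the Protocol.

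- **Section 15 (Practice Exams), who is examined.** The volunteers are "adult volunteers who are not enrolled in the GuLF STUDY". On numbers, one sentence says "About 20 participants age 21 or older will be invited to take part in practice exams" and another says "Up to twenty-five practice exams will be completed at each site".
- **Section 15, what is done.** "Exams will be conducted using the procedures described above". Staff also "provide participants with reports, referrals and remuneration".
- **Section 15, contact details.** Only minimal details are recorded, and then: "Contact information will be destroyed upon completion of the practice exam and the stored data and samples will be anonymized".
- **Section 6, Table 1.** The mental health component is listed as "Questionnaire administration and referral, if needed".
- **Section 6.10 (Mental Health Assessment).** Referral is given in real time, by validated cutoffs on the PHQ-9, PC-PTSD and GAD-7. It then says: "Follow-up calls will be placed to all participants who receive a mental health referral". The call has two purposes: to find out whether services were obtained and to give more information about services if needed.
- **Section 6.10, Table 3.** Each of the four rows on suicidal or homicidal thoughts includes a follow-up call.

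**The concern.** The two instructions cannot both be followed for the same person. The call asks what happened after the visit, so it has to be placed after the exam. By then Section 15 has had the contact details destroyed. The volunteers are outside the cohort, so there is no cohort contact file to fall back on.

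What is at stake is participant safety. The clearest case is the Table 3 row for a person who voices suicidal thoughts, is judged not to be in imminent danger, may finish the exam and goes home. For that person the call is the plan's stated check that care was reached. Section 15 removes it without saying so.

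**Working it through.** The plan states no figure to reproduce and no statistical calculation applies. The check sets the sections side by side and then counts who can be affected.

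**1. Does the call apply to practice volunteers?** Section 15 imports the exam procedures and names referrals among the staff's tasks. It also calls the volunteers participants, the word Section 6.10 uses for those who must be called. On the text, the duty reaches them.

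**2. Order of events when an exam is completed.**
- The mental health assessment is done near the end of the exam (Section 6.10).
- A referral is given on the spot if a cutoff is met.
- The exam is completed.
- Contact details are destroyed (Section 15).
- The follow-up call falls due, with nothing left to place it with.

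**3. Is there another route for staff to reach the volunteer?** Section 15 describes a consent form signed by a staff member and a witness and marked with a participant ID. It describes no retained contact record. The practice-exam consent itself is not in the document and could not be checked.

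**4. Which situations lose the call?**

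| Situation | Study activities | Follow-up call required | Can the call be made as written? |
|---|---|---|---|
| Referral by questionnaire cutoff, exam completed | continue | yes | no |
| Table 3, self, no imminent danger, exam completed | may continue | yes | no |
| Table 3, other, no imminent danger, exam completed | may continue | yes | no |
| Table 3, self, imminent danger | end | yes | unclear |
| Table 3, other, imminent danger | end | yes | unclear |

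The call is required in 4 of 4 Table 3 rows. It is lost in 2 of them when the exam is completed. In the other 2, study activities stop early, and Section 15 does not say whether completion is then reached. If such an event needs a call to 911, local authorities or social services, Section 13 separately requires the IRB report to cover the outcome of the actions taken. No loss is claimed for these two rows.

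**5. Size.**
- Planned volunteers: about 20.
- Ceiling: 2 sites × 25 exams = 50.
- The document gives no referral rate. As scaling only, each 10% referred would be 0.10 × 20 = 2 volunteers, or 0.10 × 50 = 5.

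**The case against.** The best reply is that specific text governs general text. Section 15 imports the exam procedures and then, in a sentence beginning with a contrast, sets out how practice exams differ: minimal contact details, destroyed at completion. A duty that depends on having contact details would naturally give way. In support, Table 1 lists no post-visit call as an exam component, and Section 15's own task list names referrals but not calls. Even so, on that reading the call is dropped for these volunteers, and Section 15 does not say that this is intended.

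Section 6.10 could also be read as covering enrolled participants only. That is arguable, but Section 15 uses the same word for the volunteers.

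Completion is undefined, so staff might treat an exam with a pending call as incomplete. Nothing in the text says so, and if that is meant, a sentence should state it. It is fair that the no-imminent-danger rows let activities continue only if the level of distress permits, which is why the claim is confined to exams that are completed.

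Section 6.1 puts staff contact details on the main consent form, and practice volunteers receive a copy of theirs. If that copy carries the same details, a volunteer could ring for further information. That serves one purpose of the call, but staff would still not learn whether care was obtained unless the volunteer chose to ring.

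Finally, prompt anonymization of people outside the cohort is a defensible privacy choice, since the exam covers suicidal ideation and illicit drug use. This stands as a reason to keep any retention short and limited to those referred.

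**Conclusion.** The concern holds, at low severity. As written, Addendum 3 requires a follow-up call after every mental health referral and also destroys the means of making it for any practice volunteer whose exam is completed. Whether this is read as a contradiction or as Section 15 overriding Section 6.10, the safety check is lost.

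It can touch only the practice volunteers: about 20 as planned, 50 at most, and among them only those referred. Referral and emergency steps during the visit are unaffected, and no statistical analysis depends on it.

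The conclusion assumes that completion means the end of the exam visit and that the unseen practice-exam consent makes no separate provision for keeping contact details.

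**What to change.** Add to Section 15, and to the practice-exam consent, wording to this effect:

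> For a volunteer who receives a mental health referral under Section 6.10 or meets any row of Table 3, including one whose exam is stopped early, the minimal contact details are kept apart from the exam data until the follow-up call is completed or a stated number of attempts (for example three) has been made. They are then destroyed, and the data and samples are anonymized. For all other volunteers, contact details are destroyed on completion of the exam.

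This also settles the imminent-danger rows, which the present text leaves open.

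The cost is two or three sentences in each document. The drawback is that a few referred volunteers stay identifiable a little longer, and the retained record itself marks them as referred. It must therefore be stored separately from the exam data, and volunteers should be told of it at consent.
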